After written consent is obtained, the pre-COVID-19 and baseline information will be collected. Their COVID-19 information will be collected via face-to-face interview or telephone follow-up or by email. 1, 3 and 6-month data post-discharge will be collected via telephone follow-up interview with the patient or e-form completed by the patient.

Quality of life assessment tools

SF-12

The 12-Item Short Form Health Survey is an abbreviated version of the 36-Item Short Form Health Survey. It is a widely used, international, validated survey for investigating health-related quality of life in a variety of both acute and chronic conditions. The survey instrument has eight domains: physical functioning, physical role, bodily pain, general health, vitality, social functioning, emotional role, and mental health. Each domain is measured on a 0-100 scale. A higher score correlates with a higher quality of life. The survey generates a Mental Component Summary (MCS) and a Physical Component Summary (PCS). A Chinese version of the survey, the 12-item Chinese (Hong Kong) Short Form Health Survey (version 2) (SF-12v2 (HK)) has been previously validated and used in Hong Kong.²¹ We will be using the four week recall (standard) version of the SF012v2(HK).

EQ-5D-5L

The EQ-5D-5L is a brief health status measure that comprises of five domains: mobility, self-care, pain, usual activities, and psychological status. EQ-5D-5L has been validated in Hong

Kong, recently for use in patients with chronic obstructive pulmonary disease.²³

Return to work status

Patients' pre-COVID-19 infection work status will be compared to their post-infection status. The type of employment, salary and each patients' subjective work experiences before and after infection will be queried.

Definitions

COVID-19 = Coronavirus Disease 2019, the new disease pandemic caused by the SARS-CoV-2 virus.

CUHK = The Chinese University of Hong Kong

EQ-5D-5L = EuroQol Five Domain survey, one of the two main survey instruments we will use to quantitatively judge quality of life for enrolled study subjects.

NTEC = New Territories East Cluster, a grouping of healthcare facilities in northeast Hong Kong.

PWH = Prince of Wales Hospital, the largest acute care hospital in the Hong Kong Hospital Authority's New Territories East Cluster as well as the major teaching hospital for the Chinese University of Hong Kong's medical school.

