SARS = Severe Acute Respiratory Syndrome, the disease associated with the coronavirus epidemic of 2003 (not to be confused with SARS-CoV-2, which is the virus causing COVID-19 disease).

SARS-CoV-2 = Severe Acute Respiratory Syndrome Coronavirus 2, the virus identified as the causative organism of the COVID-19 disease.

SF-12 = The 12-Item Short Form Health Survey, one of the two main survey instruments we will use to quantitatively judge quality of life for enrolled study subjects. We will use the SF-12v2(HK) version of the SF-12, which has been specifically validated for use in Hong Kong.

Study design

Recruitment

All adult COVID-19 patients aged ≥ 18 years who present to the infectious diseases specialist outpatient follow-up clinic at PWH will be screened for inclusion in this study by research assistants involved in this study.

First interview

After consent, the pre-COVID-19 assessments of SF-12v2(HK) and EQ-5D-5L will be obtained

by face-to-face interview or by phone interview by a research assistant or by e-form completed by the patient. The interview process should take no longer than 10 minutes. The questionnaire may be completed by a proxy if the patient is unable to respond to the interviewer. Work status one month prior to COVID-19 diagnosis will be determined at this time as well.

Follow-up interviews

The SF-12v2(HK) and EQ-5D-5L will be obtained by telephone interview from the patient or e-form completed by the patient. The follow-up measures will be performed at 1, 3, and 6-months after date of recovery by a research assistant.

Studies have found differences between quality of life assessments completed by the patient or by proxy. In previous studies, it has been shown that when using EQ-5D-5L as an assessment tool, there is good agreement on the domain of self-care, but only a “fair” agreement on domains such as mobility, pain and anxiety were observed between the patients and caregiver rating.²⁴ However, if all proxy responses were excluded, quality of life for survivors of sepsis with communication problems would not be included, which would be a significant methodological and ethical problem. Thus, in this proposed study, the questionnaire may be completed by a proxy if the patient is unable to respond to the interviewer (e.g. patients with dementia or stroke). A subgroup analysis will be performed accordingly.

Data processing and analysis

Outcomes

Primary outcome

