The primary outcome measure will be the health summary scores from SF-12v2(HK) in COVID patients at six-months post-discharge from hospital.

Secondary outcomes

The secondary outcome measures will include the health status measures of the EQ-5D-5L and return to work status in COVID patients at six-months post discharge from hospital.

Other measures

The required clinical data for patient characteristics and data for investigating each patient’s relative illness severity will be collected at the earliest opportunity after subject enrollment. The final COVID-19 diagnosis and any other final diagnoses will be recorded from the patient’s existing clinical notes. The Hospital Authority’s computerized Clinical Management System (the

system used by all hospitals under Hospital Authority for storing and retrieving patients' data) will be reviewed to identify hospital admissions, emergency department reattendance, lengths of stay (intensive care, step-down units or general wards) and mortality.

Statistical analysis

General

Chi-square and Fisher's exact tests will be used for categorical data while t-tests will be used to compare means of continuous variables. A p value <0.05 will be considered statistically significant and all tests will be two-tailed.

Primary analysis

A univariate and multivariate analysis of the data set will be conducted at six months. SF-12v2 dimensions of survivors of COVID-19 will be compared with data from past survivors of SARS infection, sepsis or trauma. We will also compare this data to the general Hong Kong population summary score data. Data from the EQ-5D-5L survey instrument will be compared using the Chi-square or Fisher's exact tests.

Secondary analyses

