COVID-19 is still an incompletely understood disease. We will perform secondary analyses on the data to allow us to focus on specific groups and to adjust for variability. We will consider the severity of COVID-19 by examining each patient's clinical record, number of hospital days admitted, number of days spent in the intensive care unit, number and severity of organ(s) dysfunction, co-infections, pathogen(s) identified, pre-COVID-19 health status and pre-existing conditions. It is anticipated that there will be marked changes and differences in health status and functional outcome depending on patient age. Comparisons of quality of life between four time points (pre-sepsis, hospital stay, 3-months and 6-months after discharge) will be assessed using paired t-test or Wilcoxon (W) tests as appropriate.

Multivariate logistic regression analysis

All parameters will be entered into a multiple logistic regression model and used to evaluate associations and account for variation. Multiple logistic regression adjusts for variable interactions and will be used to identify predictors of quality of life in COVID-19 patients during follow-up.

References

1. World Health Organization. *Situation Report-78 HIGHLIGHTS.*; 2020. https://www.who.int/docs/default-source/coronavirus/situation-reports/20200407-sitrep-78-covid-19.pdf?sfvrsn=bc43e1b_2. Accessed April 10, 2020.
2. Centre for Health Protection of the Department of Health of the Hong Kong SAR. *Countries/Areas with Reported Cases of Coronavirus Disease-2019 (COVID-19).*; 2020. https://www.chp.gov.hk/files/pdf/statistics_of_the_cases_novel_coronavirus_infection_en.pdf. Accessed April 10, 2020.
5. Hui DS. Severe acute respiratory syndrome (SARS): Lessons learnt in Hong Kong. *J Thorac Dis.* 2013;5(SUPPL.2). doi:10.3978/j.issn.2072-1439.2013.06.18

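### The primary six-month comparison with Hong Kong norms in effect uses only patients who have a six-month score, although earlier scores that could reduce bias from health-related loss are scheduled

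*Combined protocol and SAP*

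**What the plan says.** The section on the primary outcome reads: "The primary outcome measure will be the health summary scores from SF-12v2(HK) in COVID patients at six-months post-discharge from hospital". Under General, "t-tests will be used to compare means of continuous variables", and "A p value <0.05 will be considered statistically significant and all tests will be two-tailed". Under Primary analysis, "A univariate and multivariate analysis of the data set will be conducted at six months", and for the norms, "We will also compare this data to the general Hong Kong population summary score data". The Hypotheses section makes this norm comparison the null hypothesis of the study.

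The same instrument is also given at other times. The First interview section schedules a pre-COVID assessment. The Methods section says "1, 3 and 6-month data post-discharge will be collected via telephone follow-up interview", with an electronic form as the alternative. The Follow-up interviews section says "The follow-up measures will be performed at 1, 3, and 6-months after date of recovery by a research assistant". Under Other measures, illness-severity data are to be gathered early after enrolment, and mortality is taken from the hospital record system.

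The comparisons between time points are placed under Secondary analyses, where they "will be assessed using paired t-test or Wilcoxon (W) tests as appropriate". The time points listed there do not include month 1. The logistic model in the last analysis section looks for predictors of quality of life during follow-up. No analysis section mentions missing scores, imputation, weighting, a longitudinal model or the handling of deaths.

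**The concern.** A t-test on six-month scores can use only patients who supply one. The mean of those patients estimates the mean of the cohort only if having a score is unrelated to health. Follow-up is remote and lasts six months, and what is being measured is health, so a link between the score and the chance of answering is plausible.

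At stake is the main result. If patients who are doing worse stop answering, a real deficit against the norm shrinks and may be missed. If patients who feel well stop answering, a deficit is exaggerated or created. A larger sample does not help: the bias stays the same while the confidence interval narrows around it. The pre-COVID, 1-month and 3-month scores carry information about those who are lost, and the plan gives them no part in the primary comparison.

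**Working it through.** **Inputs from the documents.** Two-sided 5% level; t-test; scores pre-COVID and at 1, 3 and 6 months; a planned sample of 100 (Methods) or about 200 (Sample size calculation). The plan has no figure for loss that could be reproduced. The 80% in the sample size section is agreement to take part, not retention: (89 + 117) × 0.80 = 165 enrolled. The illustration below uses 100; the bias does not depend on this choice.

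**Assumed inputs (none is in the documents).** SD 10; correlation between visits 0.5 to 0.7; log odds ratio of loss 0.5 to 1.0 per SD lower three-month score, which is an odds ratio of about 1.6 to 2.7; loss at six months of 10, 20 or 30%.

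**Bias of the observed-only mean.** With d the proportion lost,

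bias = d × (mean of responders − mean of non-responders).

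At correlation 0.7 and log odds ratio 1.0, the simulated gap is about 6 points:
- 10% loss: 0.10 × 6.28 = 0.63
- 20% loss: 0.20 × 6.08 = 1.22
- 30% loss: 0.30 × 5.89 = 1.77

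Across the assumed range (simulation, 2,000 runs per setting):

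| Loss | Bias of observed-only mean (points) |
|---|---|
| 10% | about 0.3 to 0.6 |
| 20% | 0.5 to 1.2 |
| 30% | 0.7 to 1.8 |

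If healthier patients are the ones lost, the sign reverses (−1.2 at 20% in the strongest setting).

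**Set against the standard error.** With 100 enrolled and 20% lost, 80 respond and SE = 10/√80 = 1.12. The largest bias at 20% is therefore 1.2/1.12 = 1.1 SE. In that setting the 95% interval covers the true mean in 81% of studies. Power to detect a true 3-point deficit against a fixed norm is 37%, compared with 76% when loss is unrelated to health. These two results belong to the strong end of the assumed range. Over the whole range at 20% loss, a test of a true null rejects in about 7% to about 20% of studies of 100 patients; at 10% loss, in about 5 to 8%. With upward bias, nearly all of these false rejections at 20 to 30% loss would show survivors as better than the norm.

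**What the earlier scores recover.** The six-month score was regressed on the three earlier scores among responders, and the prediction was averaged over all patients:
- Loss explained by the recorded three-month score: remaining bias at most about 0.05 points.
- Patients who miss month 6 also miss month 3: about 0.1 to 0.5 points remain at 20 to 30% loss.
- Loss depends on the six-month score itself (20% loss, log odds ratio 1.0): a bias of 1.7 falls to 1.1 at correlation 0.5 and to 0.8 at correlation 0.7.

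The correction is therefore complete only in the first case.

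**The case against.** Several points on the other side are fair.

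- A reader might infer that the plan prescribes a complete-case analysis. It does not say so. The reading follows from a t-test at six months with no other method stated. The plan's word for a multivariate analysis is not specified further and does not fill the gap.
- A reader might infer that the result will overstate quality of life. The documents give no loss rate and no evidence on who is lost, so neither size nor direction is known. At 10% loss the bias is modest.
- A reader might take substantial loss as certain. The plan has safeguards: patients must agree to six months of follow-up, those not reachable by telephone at the scheduled times are excluded, and a proxy may answer for a patient who cannot. These make heavy health-related loss less likely. They do not correct for loss after enrolment.
- A reader might think that the paired tests also discard everyone without a six-month score. They do not: a pair made of the pre-illness and 3-month scores keeps such patients. Those tests are secondary in any case.
- A reader might expect the earlier scores to cure the problem. The remaining bias shown above contradicts this. In addition, patients are recruited at a post-discharge clinic, so some may have no month-1 score, and the pre-COVID score is recalled after the illness.

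None of this is a reason to keep the observed-only t-test as the primary method. The alternative uses data already scheduled. In the settings examined, its bias was smaller than that of the t-test wherever loss was related to health, and it adds none where loss is unrelated to health.

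**Conclusion.** The point stands as a cheap improvement, not as a demonstrated error. As written, the primary comparison with norms in effect rests on patients who have a six-month score and leaves out earlier information on those who do not. The possible bias is about 0.3 to 1.8 points over 10 to 30% loss, in a direction that cannot be fixed in advance. This size rests wholly on the assumed SD, correlation, loss rate and strength of the link between health and loss. Using the earlier scores removes nearly all of the bias if recorded data explain the loss, and only part of it if month 3 is missing too or if loss depends on the six-month score itself.

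**What to change.** In the Primary analysis section:

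1. Estimate the six-month PCS and MCS means among patients alive at six months, and compare these means with the norms. Use a likelihood-based repeated-measures model over all available pre-COVID, 1-, 3- and 6-month scores with age, sex and severity, or multiple imputation with the same variables.
2. Report deaths before six months separately and do not impute scores for them, because the aim concerns survivors.
3. Report six-month non-response by earlier score.
4. Give two sensitivity analyses: the t-test on observed scores, and a delta-adjusted analysis in which missing scores are not missing at random.

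The time origin of the visits should be stated once, since the Methods section counts from discharge and the Follow-up interviews section from recovery.

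Cost: about one paragraph and slightly more analysis work, with no new data. The downside is reliance on loss being explained by recorded data, which the delta-adjusted analysis is there to test.

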Several instruments have been widely used in quality of life research, including the 36-Item Short Form Health Survey (SF-36), the 12-Item Short Form Health Survey (SF-12), the World Health Organization Quality of Life Instruments (WHOQOL-BREF), EuroQoL-5D (EQ-5D-5L) and the Short-Form Six-Dimension (SF-6D). Our team has experience using the SF-36, SF-12v2(HK) and the EQ-5D-5L survey instruments for monitoring quality of life in research subjects in Hong Kong. For example, we found that trauma patients in Hong Kong scored significantly worse on the SF-36 twelve months after injury.¹⁷ We also found the most dramatic improvements happened in the first one to six months post-injury,¹⁹ and that 45% of subjects had achieved an excellent outcome by four years post-injury.²⁰ The SF-12v2(HK) with four week recall is a modified version of the SF-36 to be shorter and quicker to use, while also already translated and validated in Hong Kong.²¹ We aim to combine our experience with conducting quantitative quality of life studies with the CUHK Department of M&T's expertise in coronavirus treatment and follow-up to explore the quality of life of COVID-19 patients in recovery.

The reported mortality rates for COVID-19 has so far been lower than SARS, although the higher absolute numbers of COVID-19 patients mean worldwide deaths are overall much higher. Trauma, sepsis and SARS survivors have all experienced significant long-term morbidity and decreased quality of life as a result of their injuries or infections. A previous study of patients infected with SARS-CoV-1 in 2003 at PWH showed that significant numbers of recovering patients had impaired long-term health status.¹² The question this study hopes to answer is to what degree do COVID-19 patients suffer a similar fate? Has the knowledge gained from the SARS experience led to improved quality of life outcomes compared to SARS survivors? Or do the similarities between the viruses that cause SARS and COVID-19 extend to a reduced quality of life after recovery as well?

Aims

This study aims to determine the quality of life of COVID-19 survivors up to six-months after discharge from hospital or quarantine. We also aim to compare the quality of life of COVID-19 survivors to baseline known Hong Kong quality of life norms.

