By identifying overall COVID-19 quality of life as well as specific associations or differences between COVID-19 and baseline local quality of life values, we hope to be able to provide evidence-based conclusions to medical practitioners trying to achieve the best quality of life for patients recovering from COVID-19.

Hypotheses

The null hypothesis is that recovered COVID-19 patients have no difference in quality of life compared to a normal control (baseline Hong Kong quality of life norms).

The alternative hypothesis is that there is a difference in quality of life measures between recovered COVID-19 patients and a normal control.

Plan of Investigation

Subjects

All adult patients aged ≥ 18 years who present to the infectious diseases specialist outpatient follow-up clinic at PWH will be screened for inclusion in this study. The inclusion criteria are age ≥ 18 years, laboratory-confirmed COVID-19 infection with SARS-CoV-2, and patients who agree to follow-up for up to six months following their first interview.

Exclusion criteria:

Patients aged below 18 years will be excluded.

Patients will be excluded if they meet ANY of the following criteria:

Patients or their next of kin are unable to communicate in Chinese or English,

Unwilling or unable to provide written informed consent,

or Patients who will not be available for telephone follow-up at the scheduled times.

We will record all patients who are not enrolled and the reasons for exclusion.

Sample size calculation

As of April 10, 2020, in the NTEC Hospital Authority cluster there have been 89 patients

admitted to PWH (of which 17 patients have already been discharged) and 117 admitted to United Christian Hospital with 42 discharged so far.²² Both PWH and United Christian Hospital's COVID-19 patients will follow-up at the PWH infectious diseases specialist outpatient follow-up clinic. Based on prior studies at PWH with SARS patients, approximately 80% agreed to participate in follow-up studies, so we will likely enroll approximately 200 COVID-19 patients.

Methods

This will be a prospective, observational, multicenter, cohort study. We plan to recruit 100 patients with laboratory confirmed COVID-19 disease who have been discharged from inpatient care or quarantine. Quality of life will be assessed using the SF-12v2(HK) and EQ-5D-5L survey instruments, and their return to work status will be measured up to six months from the date of discharge.

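### The plan tests its only null by comparing six-month SF-12v2(HK) scores with Hong Kong population scores but specifies no age/sex standardisation, so case mix could create or hide a difference

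*Combined protocol and SAP*

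**What the plan says.** **Null and aim.** Under Hypotheses, the null is that "recovered COVID-19 patients have no difference in quality of life compared to a normal control (baseline Hong Kong quality of life norms"). The Aims section agrees: "We also aim to compare the quality of life of COVID-19 survivors to baseline known Hong Kong quality of life norms".

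**Outcome.** Under Primary outcome: "The primary outcome measure will be the health summary scores from SF-12v2(HK) in COVID patients at six-months post-discharge from hospital".

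**Analysis.** Under Statistical analysis, General, the rule is that "t-tests will be used to compare means of continuous variables", two-tailed at p<0.05. Primary analysis opens with "A univariate and multivariate analysis of the data set will be conducted at six months", then says "SF-12v2 dimensions of survivors of COVID-19 will be compared with data from past survivors of SARS infection, sepsis or trauma", and then "We will also compare this data to the general Hong Kong population summary score data". Nothing else in the document describes the comparison with norms.

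**Sample.** Under Subjects, all adults of 18 or over attending the infectious diseases follow-up clinic are screened. No age or sex quota or matching is given.

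**Age and adjustment.** Secondary analyses anticipates marked differences in health status and functional outcome by patient age, and states a general wish to adjust for variability. The logistic regression section looks for predictors of quality of life among COVID-19 patients.

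**The concern.** The comparison with norms is the only analysis that answers the stated null. Its reference is external: population scores from people whose age and sex mix may differ from that of clinic attenders. If the summary scores depend on age or sex and the two mixes differ, a comparison with an overall norm mean estimates two things at once: the effect of COVID-19 and the effect of being an older or younger, more or less female group than the reference.

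An older cohort could show a deficit that has nothing to do with infection. A younger one could conceal a real deficit. More patients do not help, because they make the estimate more precise around the wrong value. The study's headline conclusion depends on this step, and the choice of norm, if left until the data are in hand, could change that conclusion.

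**Working it through.** **1. Is there any standardisation in the plan?** The candidates, set side by side:

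- *The univariate and multivariate analysis* (Primary analysis): no model, no covariates, and no link to the norm comparison.
- *Adjusting for variability* (Secondary analyses): placed among secondary analyses and not tied to the norms.
- *Logistic regression*: looks for predictors within the COVID-19 cohort. A model fitted to patients alone cannot align them with an outside population unless stratified norms or a reference mix are brought in.
- *Paired comparisons over time* (Secondary analyses): free of age/sex mix, but they test change within patients, not the null against norms.

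None specifies how age and sex enter the norm comparison.

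**2. Sample sizes.** The plan has no power calculation, SD, norm value or age distribution, so it has no figure of its own to reproduce for this comparison. It gives two sample sizes: about 200 (Sample size calculation) and 100 (Methods). The stated inputs give (89 + 117) × 0.80 = 164.8, about 165, which is neither. I therefore show 100, 165 and 200.

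**3. Illustration.** All of these are assumptions: two age bands; older share 30% in the norm and 50% in patients; within-band SD 1; age gap d = 0.25, 0.5 or 1.0 within-band SD; no true effect; norm treated as fixed.

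- Shift in the mean = (0.50 − 0.30) × d = 0.05, 0.10, 0.20.
- Patients' total SD = √(1 + 0.5 × 0.5 × d²) = 1.008, 1.031, 1.118.
- Rejection rate ≈ Φ(−1.96 + k) + Φ(−1.96 − k), where k = shift × √n / total SD.

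| d | n=100: k, rate | n=165: k, rate | n=200: k, rate |
|---|---|---|---|
| 0.25 | 0.50, 7.9% | 0.64, 9.8% | 0.70, 10.8% |
| 0.5 | 0.97, 16.3% | 1.25, 23.8% | 1.37, 27.9% |
| 1.0 | 1.79, 43.2% | 2.30, 63.2% | 2.53, 71.6% |

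A simulation with the t-test (40,000 replicates) agrees: 7.9%, 15.9% and 42.5% at n=100, and 10.6%, 27.5% and 71.1% at n=200. After subtracting the band norm, the rate is 5.0% to 5.2% throughout.

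**4. Masking.** The same arithmetic works in the other direction. With an older share of 10% in patients against 30% in the norm and d = 0.5, the shift is 0.10 in the patients' favour. A true deficit of 0.10 would then be cancelled exactly.

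**5. Norm sampling error.** With the same mix in both groups, counting it widens the CI by √(1 + n/m), where m is the norm sample size. For an assumed m = 1,000 this is √1.1 = 1.049 at n=100 and √1.2 = 1.095 at n=200. If it is ignored, a nominal 5% test has a true error rate of about 6% at n=100 and 7% at n=200.

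**The case against.** The strongest reply is that the plan is silent rather than crude. It never says that the norm is a single overall mean, and the same short paragraph promises a multivariate analysis. That stands. A reader might infer that the investigators have chosen an unadjusted comparison, or that the t-test is prescribed for it. The documents support neither: the t-test sentence is a general rule, and no method is named for the norm comparison. What remains is that nothing in the plan ties any adjustment to the test of its own null.

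A second reply is that the age sentence appears in a paragraph about severity and patient groups and does not say that SF-12v2 norms vary by age. That also stands. It makes age dependence plausible on the plan's own terms, but it does not show that the bias is material.

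A reader might also infer larger error rates by treating the 1.0 SD gap as a shift of 0.20 total SD, which gives 52% at n=100 and 81% at n=200. That ignores the wider spread created by the age mix itself. The rates in the table are the right ones for these assumptions.

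Finally, the pre-COVID scores and paired tests offer a contrast free of age/sex mix. This is partial mitigation only: it answers a different question, and the scores are recalled, being collected after consent at the follow-up clinic.

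**Conclusion.** The point holds as a gap in the specification of the primary comparison, and it should be fixed. The null is addressed by one sentence that specifies no age/sex standardisation, in a sample not matched to the reference.

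Under the stated assumptions the false-rejection rate runs from about 8% to 42% at n=100 and from 11% to 71% at n=200, against a nominal 5%. The upper values need an age gap of a full within-band SD. The documents give no norm gradient and no cohort age or sex mix, so whether the bias would be material, and in which direction, is unknown. They do not support a claim that the result will be biased.

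Nor does standardisation turn the comparison into a clean COVID-19 effect. The return to about 5% in the simulation covers only the age band that was modelled. Comorbidity and other differences between patients and the general population remain.

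**What to change.** In Primary analysis, state the following.

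- PCS and MCS at six months will be compared with age- and sex-specific Hong Kong norms. For each patient, subtract the norm mean of that patient's age-sex band, and report the mean difference with a 95% CI.
- The CI will include the norms' sampling error where it is published, by adding to the variance of the mean difference the sum over bands of (patient share)² × norm variance / norm band size. Otherwise the plan will say that the norms are treated as fixed.
- If only an overall norm mean is available but the norm sample's age/sex mix is known, the cohort will be reweighted to that mix. If the mix is not known, the comparison will be labelled descriptive.
- As a check, the same comparison will be applied to the pre-COVID SF-12v2(HK) scores, noting that they are recalled. A gap there would point to residual case mix or recall error.

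**Cost.** Plan wording and a norms lookup. No new patient contact should be needed, since Other measures already covers "The required clinical data for patient characteristics". The CI is about 5% wider at n=100 and 10% wider at n=200 if norm error is counted for an assumed norm sample of 1,000. Reweighting also costs precision: in the two-band illustration the weights are 0.7/0.5 = 1.4 and 0.3/0.5 = 0.6, so the CI widens by about √(0.5 × 1.4² + 0.5 × 0.6²) = 1.08. The main dependence is on stratified norms, which the documents do not confirm exist. That is why the fallbacks should be written in now.

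### The six-month EQ-5D-5L comparison names only Chi-square or Fisher's exact tests, which ignore the severity order of the domain levels; an ordered analysis would be a cheap improvement

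*Combined protocol and SAP*

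**What the plan says.** Secondary outcomes lists the endpoint: "The secondary outcome measures will include the health status measures of the EQ-5D-5L and return to work status", at six months after discharge. The instrument is described under Quality of life assessment tools: "The EQ-5D-5L is a brief health status measure that comprises of five domains: mobility, self-care, pain, usual activities, and psychological status".

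The test is fixed in Statistical analysis, Primary analysis: "Data from the EQ-5D-5L survey instrument will be compared using the Chi-square or" Fisher's exact tests. The General paragraph has two classes of data and no rule for ordinal responses: Chi-square and Fisher's "exact tests will be used for categorical data while t-tests will be used to compare means of continuous variables". The significance rule is "A p value <0.05 will be considered statistically significant and all tests will be two-tailed".

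Secondary analyses adds that comparisons of quality of life between time points, up to "6-months after discharge) will be assessed using paired t-test or Wilcoxon (W) tests as appropriate". This rule is not restricted to the SF-12. The last analysis paragraph plans a multiple logistic regression for predictors of quality of life, without saying how the outcome is coded.

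Four things are not stated: the comparator for EQ-5D-5L, whether the response levels are kept or pooled, whether an index is scored, and what effect or power is expected.

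**The concern.** A domain such as mobility or pain is answered on graded levels of severity. A Pearson Chi-square or Fisher test on those levels gives the same p-value if the levels are shuffled. If survivors are somewhat worse across the whole scale, the evidence is spread over up to four degrees of freedom, where an ordered test concentrates it in one.

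The study asks to what degree survivors are impaired, and whether they fare better or worse than others. An omnibus p-value answers neither part, and the plan promises no effect estimate or confidence interval for EQ-5D-5L. At stake is a secondary endpoint that could miss a consistent shift towards worse health, in a cohort whose size is limited by local admissions.

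**Working it through.** **Inputs from the documents.** Two-sided 0.05 (General); Chi-square or Fisher (Primary analysis); 100 patients (Methods) or about 200 (Sample size calculation). No power, effect or response distribution is stated for any endpoint, so there is no plan figure to reproduce.

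**Assumptions, not in the documents.** Five ordered levels per domain; a comparator group as large as the cohort; a proportional-odds shift with cumulative odds ratio (OR) 2. The reference percentages across the five levels are A 85/10/3/1.5/0.5, B 70/20/7/2/1 and C 50/30/13/5/2. As an example of the shift, in A the odds of no problem are 0.85/0.15 = 5.67; halved, they are 2.83, so the share at no problem falls to 2.83/3.83 = 74%.

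**Step 1: degrees of freedom.** For 80% power at two-sided 0.05, the noncentrality needed is 7.85 on 1 df and 11.94 on 4 df. The ratio is 11.94/7.85 = 1.52, or about 52% more patients. At noncentrality 7.85 the 4-df test has 60% power. The loss is therefore about 20 points if the ordered test captures the whole effect.

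**Step 2: simulated power per domain, 100 per group, OR 2 (3,000 runs).**

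| Reference | Five-level Chi-square | None vs any Chi-square | Rank-sum | Loss, five-level | Loss, none vs any |
|---|---|---|---|---|---|
| A | 28.8% | 50.8% | 50.7% | 21.9 | -0.1 |
| B | 45.5% | 66.9% | 69.3% | 23.8 | 2.4 |
| C | 50.9% | 67.4% | 74.1% | 23.2 | 6.7 |

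A separate rerun gave 28/44/54% for the five-level Chi-square against 50/68/76% for rank-sum, which is a loss of 22, 24 and 22 points. Across reruns the none-versus-any loss was about 0 to 9 points.

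**Step 3: pooling and Fisher.** In a smaller run (600 per setting) with the three upper levels pooled, Chi-square gave 44/62/68% against rank-sum 53/72/79%, a loss of 9, 10 and 11 points. In the same run the exact Fisher test on five levels gave 37/53/59%, a loss of 16, 19 and 20 points.

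**Step 4: other sizes and distributions (20,000 runs, OR 2).** Each cell shows five-level Chi-square, then rank-sum.

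| At no problem | 100 per group | 165 per group | 200 per group |
|---|---|---|---|
| 85% | 28%, 50% | 48%, 71% | 58%, 80% |
| 60% | 50%, 73% | 76%, 91% | 85%, 96% |
| 40% | 56%, 77% | 80%, 94% | 89%, 97% |

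The size 165 is 80% of the 89 + 117 = 206 admissions quoted. The gap narrows as rank-sum power nears its ceiling. With 40% at no problem and 100 per group, collapsing to none versus any is costlier: 62% against 77%, about 15 points.

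**Step 5: type I error.** At OR 1 the two-group Chi-square rejected in about 2% to 5% of runs.

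**Step 6: where the loss shrinks or reverses.** Against fixed norms (one sample, OR 1.5 to 2) the loss was about 0 to 16 points. With 97% at no problem and n = 100 there was no loss, but the Chi-square type I error was then about 13%. In one example of a change that was not one-directional (n = 165), Chi-square had 85% power and rank-sum 11%.

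**The case against.** The strongest reply is that the loss belongs to one reading of an unspecified comparison. The sentence names no comparator: the SARS, sepsis, trauma and Hong Kong norm comparisons appear in sentences about SF-12v2 dimensions and the general population summary scores. It also does not say that all five levels are tested. A none-versus-any table fits the same sentence and loses little when most patients report no problem. Against fixed norms the loss is smaller, and exact Fisher does somewhat better than Pearson. All of this stands, and it is why the size is conditional.

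A reader might infer four stronger claims that the documents do not support:

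- *EQ-5D-5L gets no ordered analysis anywhere.* Not so. The paired t-test or Wilcoxon rule refers to quality of life generally and can include EQ-5D-5L; both tests use order and show direction. But a paired rule cannot compare survivors with another population. If the Primary analysis sentence instead meant before and after in the same patients, it would ignore the pairing and conflict with that rule.
- *The test is invalid.* Two-group type I error is controlled. The inflation in Step 6 is confined to a fixed-norm test with very small expected counts.
- *A positive result says nothing about direction.* The p-value does not, but the level percentages behind it would. A rank-sum p-value alone gives no readily interpretable effect size either; the proportional-odds model does.
- *An ordered test costs nothing.* It loses power for changes that are not one-directional, and it needs level-by-level comparator counts, which the documents do not show to exist.

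**Conclusion.** The point holds as a cheap improvement to a secondary endpoint. For the six-month EQ-5D-5L comparison the plan names only tests that ignore severity order, and nothing elsewhere supplies an ordered test for it. The issue is efficiency and interpretability, not validity.

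Under a one-direction shift (two groups of 100, cumulative OR 2, 50% to 85% at no problem), the loss against rank-sum is about 20 to 25 points with a five-level Pearson Chi-square and about 16 to 20 with exact Fisher. It is about 10 points with the top levels pooled and about 0 to 9 points for none versus any. No figure can be attached to the plan unconditionally, because the comparator, coding, distribution and effect are all unstated.

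**What to change.** Replace the EQ-5D-5L sentence with text along these lines:

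> At six months, each EQ-5D-5L domain will be compared with [named comparator] by a proportional-odds model, reporting the odds ratio with its 95% CI, or by the Wilcoxon rank-sum test, where level-by-level comparator data are available. A table of any problem versus none, tested by Chi-square or Fisher's exact test, will be supportive; it will be the main comparison where only such proportions are available for the comparator.

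State the level coding beside it, including any pooling of sparse levels, and add an ordinal class to the General rule on tests. The model is the better first choice because it supplies direction and size.

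The cost is a few lines in the analysis section and no new patient data. The price is less power for a change that is not one-directional, and the need to confirm before analysis that level-by-level comparator counts can be obtained.
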